#### **Inclusion and Exclusion Criteria:**

Participants include both students, counselors, and administrative staff members of the University of Illinois at Chicago and Northern Illinois University. Students, to be included in all phases of the study, will be 18 years of age or older, English-speaking, familiar with smartphones, and living in the university communities (e.g. not studying abroad). Counselors and administrative staff members will be current employees at the University of Illinois at Chicago Counseling Center or at Northern Illinois University's Counseling & Consultation Services. Potential participants for Phase 1 will be excluded for visual, hearing, voice, or motor impairment that would prevent completion of the study procedures or use of mobile phone; diagnosis of a psychotic disorder, dissociative disorder, or other diagnosis for which participation in this trial is inappropriate, or severe suicidality (has ideation, plan, and intent). For Phase 1, Stages III and IV, student participants will have clinically elevated symptoms (defined by scores  $\geq 10$  on the PHQ-9 or GAD-7). For Phase 1, Stage V, half of the participants will have elevated symptoms of depression or anxiety as measured by scores  $\geq 10$  on either the PHQ-9 or GAD-7, and half of the participants will not have elevated scores on either measure. Participants in Phase 1, Stage V will also need to own an Android-operating or iOS-operating smartphone with a system that operates Android 7 or higher or iOS 11 or higher.

For Phase 2, students must own a smartphone device compatible with the mobile app (an Android-operating or iOS-operating smartphone with a system that operates Android 7 or higher or iOS 11 or higher). During Phase 2, we will also conduct feedback interviews with students who have not used the program. Because Black male students have been the

demographic group who appear least likely to engage with the program, we are recruiting Black male students aged 18-35 years who have not used the program to provide feedback on what they are looking for in technology-based mental health and wellness resources. Therefore, students to be included will be those who self-identify as Black/African American men, between the ages of 18 and 35, English-speaking, familiar with smartphones, and enrolled at University of Illinois at Chicago and Northern Illinois University.

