## Study Protocol:

### Objectives:

This research project aims to develop and test a Student Stress Management (SSM) mobile program, a suite of apps based within the framework of an evidence-based treatment for depression and anxiety that will be integrated within a student health system. This program will improve engagement with mental health services by serving as an access point to mental health treatment options, and providing an opportunity for self-guided treatment. The SSM program will feature components known to be effective both for engagement (symptom assessment and promotion of care accessibility) and treatment (thought restructuring, relaxation exercises, and behavioral activation). Within the suite, students will be prompted to complete symptom assessments on a weekly basis, and those with elevated symptom scores will be provided with feedback and recommendations for on-campus services. All users will be able to access and use interactive treatment apps. The program will be developed with the University of Illinois at Chicago (UIC) and Northern Illinois University (NIU) counseling centers, and will be made available to all UIC and NIU students. These studies will establish a research program that will expand the reach of services and ease the burden of untreated depression and anxiety for college students.

**Phase 1 Aim: Develop the SSM program by refining a mobile smartphone intervention and develop an optimized multi-component implementation strategy using a user-centered design process.** We will start from a suite of apps developed for a general population and, based on needs reported by current students and mental health care providers, they will be optimized for the college student population alongside development of an implementation plan and evaluation metrics. Laboratory-based usability testing and an 8-week field trial will be included as part of the iterative design process to ensure that SSM works optimally both in individual interactions, as well as cumulatively over time.

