**The following populations will be excluded from the study:**

- a. Adults unable to consent
- b. Individuals who are not yet adults (minors): infants, children, teenagers
- c. Pregnant women (where the activities of the research may affect the pregnancy or the fetus.)
- d. Prisoners or other detained individuals.

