**Resources Available:**

The PI, [name], is a licensed clinical psychologist and research assistant professor within the Department of Preventive Medicine. [name] has training and expertise in mobile and web-based interventions, and more recently, has begun working on methods to leverage technologies to expand mental health care accessibility for university students. [name] has built strong relationships with the directors of the UIC and NIU counseling centers. The mobile app programmer who is scheduled to work on this project has several years of experience building mobile mental health apps, and has collaborated with researchers from the Center for Behavioral Intervention Technologies for the past 10 years.

Both universities involved in this study have large student bodies, and serve more than 1,000 students per year. Based on the size of these student bodies, it is expected that it will be

feasible to recruit the 68 participants proposed in Phase 1 to conduct user centered design work. In Phase 2, we are interested in assessing the uptake of the intervention program and do not have a set number of participants to recruit.

The PI and a research assistant devote full-time effort to this research project. The PI and research assistant have designated office space within the Center for Behavioral Intervention Technologies, along with a personal computer and have access to a printer and scanner (available software includes SPSS/SAS, MS Office, Adobe, etc.). Both have access to research databases, administrative support, hardware, and software assistance available directly within the Department. The Department has a secure server with data security features ensuring confidentiality of participant data. All laptops are encrypted and the network has firewall protection. In addition, Northwestern University's information technology program supports researchers with the software, hardware, and data storage and retrieval facilities to conduct large-scale projects.

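### Phase 1 field-trial users are not excluded, flagged or separately analysed in the Phase 2 user cohort, so some Hypothesis 2 baselines may follow earlier use (minor)

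*Combined protocol and SAP*

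**What the plan says.** All references are to the combined protocol and SAP.

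- **Inclusion and Exclusion Criteria.** The population for the whole study is defined once: "Participants include both students, counselors, and administrative staff members of the University of Illinois at Chicago and Northern Illinois University". The student criteria are common to all phases: "Students, to be included in all phases of the study, will be 18 years of age or older, English-speaking, familiar with smartphones", plus living in the university community. For app users in Phase 2 one condition is added: "For Phase 2, students must own a smartphone device compatible with the mobile app".
- **List of excluded populations.** Under "The following populations will be excluded from the study" the document names adults unable to consent, minors, pregnant women (conditionally) and prisoners or detainees. Earlier participation and earlier app use are not on the list.
- **Objectives, Phase 1 Aim.** "Laboratory-based usability testing and an 8-week field trial will be included as part of the iterative design process".
- **Resources Available.** The Phase 1 total appears in the statement that it should be "feasible to recruit the 68 participants proposed in Phase 1 to conduct user centered design work". Phase 2 has no target number.
- **Objectives, opening paragraph.** The finished program "will be made available to all UIC and NIU students".
- **Procedures Involved, SSM Program paragraph.** The PHQ-8 and GAD-7 are first prompted when the app is downloaded.
- **Statistical Analysis Plan.** Symptoms are modelled from baseline to week 8, and literacy and coping from baseline to month 2, with multiple imputation and mixed models. Phase 1 participation is not mentioned.

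Prior use matters in one place only, the Phase 2 feedback component: "we will also conduct feedback interviews with students who have not used the program". That rule governs an interview subsample, not the app-user cohort.

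**The concern.** Hypothesis 2 concerns change in individual users after they take up the program, and a baseline is useful for that purpose only if it precedes exposure. A student who spent up to 8 weeks with the program in Phase 1 and then downloads it in Phase 2 gives a first Phase 2 score that is not a pre-exposure score. The individual-level analysis has no control group, so nothing in the comparison would absorb the difference.

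The direction cannot be fixed in advance. If Phase 1 use helped, symptoms would start lower and literacy and coping higher, leaving less room to change and pulling the estimate towards nil. If the students who return are the more engaged ones, the estimate could move the other way.

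A secondary matter is interpretation of the uptake count. A registration by someone who already knew the program from Phase 1 says less about the reach of the implementation plan than a registration by someone new to it.

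**Working it through.** The plan gives no sample-size or power figure bearing on this, so there is nothing of its own to reproduce. The check is a reading of the eligibility rules followed by simple arithmetic on the reported counts.

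**Step 1: is there a rule?**

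| Section | Rule on Phase 1 participants or prior users |
|---|---|
| Inclusion and Exclusion Criteria, common student criteria | none |
| Inclusion and Exclusion Criteria, Phase 2 app users | compatible phone only |
| Inclusion and Exclusion Criteria, Phase 2 feedback interviews | non-use required, interviews only |
| Excluded populations | none |
| Study-Wide Recruitment Methods | none; one set of channels across the study |
| Procedures Involved | none |
| Statistical Analysis Plan | no exclusion, flag or sensitivity analysis |

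**Step 2: how many users carry the Hypothesis 2 information?** Counts from the Statistical Analysis Plan, ordered from one to six assessments:

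- GAD-7: 48 + 16 + 3 + 5 + 5 + 2 = 79 with any score.
- PHQ: 48 + 17 + 2 + 5 + 5 + 2 = 79 with any score.
- Two or more scores: 79 − 48 = 31 on each measure, or 31/79 = 39.2%.

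**Step 3: how would overlap act?** Let f be the share of analysed users with Phase 1 exposure, Δ_new the mean change in first-time users and Δ_prior the mean change in returning users. In a simple average,

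observed change = (1 − f)·Δ_new + f·Δ_prior,

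so the bias relative to first-time users is f·(Δ_prior − Δ_new). The documents give neither f nor the bracketed difference, and the sign of the difference is open. Among the 31, one returning user gives f = 1/31 = 3.2%, and five (an assumed number) give 5/31 = 16.1%. The planned mixed models with imputation will not weight users equally, so these shares are only a guide.

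**Step 4: range under assumptions.** The field-trial size and the return rate are not stated. Assume 10 to 30 field-trial students, of whom 10% to 50% register again, so k = 1 to 15:

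- Share of the 117 registered users: 1/117 = 0.9% to 15/117 = 12.8%.
- Share of the 79 with any score, if all k gave scores: 1/79 = 1.3% to 15/79 = 19.0%.
- Registration among consenters is 117/(117 + 65) = 117/182 = 64.3%. Without the k students it is (117 − k)/(182 − k), that is 116/181 = 64.1% to 102/167 = 61.1%.

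The arithmetic ceiling, with all 68 Phase 1 participants registering, is 68/117 = 58.1%. It is not realistic: the 68 covers the whole of Phase 1, the study also enrols counselors and staff, and only field-trial students had the 8-week exposure.

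**The case against.** The strongest reply is that this is a possibility and not an event. No section reports a Phase 1 student in Phase 2. The interval between phases is not given, and some students may have graduated. All of that stands, and it limits the point to a gap in the plan with an unknown consequence.

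It can also be said that the program is deliberately open to every student and that penetration is illustrated by app downloads, without restriction to people new to it. This stands too. A reader might infer that uptake is overstated, but the documents do not support that. A former tester who downloads the released version is still a campus user, and whether to count that person is a choice of estimand.

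Two further inferences are tempting and also unsupported:

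- That returning users would be over-represented among the 31 with repeated scores. Nothing shows this, and it could run the other way, since these students had already seen the content.
- That field-trial students were half selected for elevated symptoms. That rule is given for Phase 1, Stage V, and no section says that Stage V is the field trial. In any case the Phase 2 baseline is measured afresh at download.

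Finally, the IntelliCare apps were already publicly available (Background), so removing Phase 1 participants would not guarantee an unexposed baseline. Hypothesis 2 also has larger weaknesses: there is no control group, 48 of 79 users have a single score and only 2 have complete data. Both remarks are fair and bear on severity. Neither removes the case for a cheap check on a known route of earlier exposure.

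**Conclusion.** The gap is real and minor. As written, the plan lets students already exposed in an 8-week field trial into an uncontrolled before-after analysis, with no means of identifying them. Where that happens, the Hypothesis 2 baseline is not a pre-exposure measurement and change from baseline is biased in an uncertain direction, possibly towards no change.

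The size cannot be determined from the documents. The ranges above rest on an assumed field-trial size and return rate, and the true overlap may be zero. The point has weight mainly because so few users have repeated scores. The aggregate counseling-center series should be little affected, since at most 68 people are involved against centers at universities described as serving more than 1,000 students a year. The conclusion does not extend to a claim that uptake is inflated.

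**What to change.** **For this cohort.**

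1. Match Phase 2 consenters to the Phase 1 participant list. Consenting students typed their names, app users registered a participant ID, and the team keeps names in separate protected files, so a match should be feasible if the Phase 1 list is still held and its consent terms allow the link.
2. Report how many overlapped, how many of those were in the field trial, and how many are among the 31 with repeated scores. A count of zero closes the question.
3. If there is overlap, fit the Hypothesis 2 models without prior field-trial users, repeating the imputation on the reduced set, or show both results.
4. Leave app access open and keep these students in the uptake count, with the overlap stated beside it.

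The Statistical Analysis Plan already reports final counts, so a new screening question comes too late here.

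**For the planned larger trial.** Add one prior-use item at screening. It would also capture earlier use of the public IntelliCare apps, which a list match cannot do.

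**Cost.** A list match, one repeat of the Hypothesis 2 models and, later, one screening item. The downside is a few fewer users, and so slightly less precision, in the analysis that omits them.

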**The following populations will be excluded from the study:**

- a. Adults unable to consent
- b. Individuals who are not yet adults (minors): infants, children, teenagers
- c. Pregnant women (where the activities of the research may affect the pregnancy or the fetus.)
- d. Prisoners or other detained individuals.

**Study-Wide Recruitment Methods:**

Participants will be recruited in-person, online, via e-mail, and via hard copy study advertisements at the University of Illinois at Chicago (UIC) and Northern Illinois University (NIU) campuses after receiving approval from administrators. After receiving permission from administrators, digital signage teaser advertisements (i.e. brief study advertisements to be displayed on televisions across campus) will be used to complement the other advertising methods. Online recruitment will be published to both public spaces and existing private groups with the permission of the private group administrators (including Facebook, Instagram and Reddit). Participants will be directed to a website with study information and from there they will be able to access the study screening form and digital consent form. Subjects agree to participate by checking a “yes” box and typing in their name. They are instructed to print out the consent form for their records. Participants are enrolled remotely to avoid excluding participants with access barriers who are among those who would be likely end users. The digital consent form will describe the mobile app program, show participants how to add a PIN to their phone, and inform participants that data entered into the phone will be de-identified to the research team, those it cannot replace the need for contacting a mental health provider in the case of an emergency. These recruitment procedures are similar to those that have been approved by the Northwestern University IRB for prior studies conducted by our lab group. For Phase 2 feedback interviews with Black male students who have not used the program, participants will be recruited online, by word-of-mouth and via e-mail at UIC and NIU campuses. After receiving IRB approval and approval from NIU and UIC study organizations, brief study advertisements and recruitment flyers will be used, as well, and published to social media platforms and through email announcements belonging to student organizations that aim to serve students, in general, and those from minority populations, e.g. student wellness, Black student associations and Greek organizations. Recruitment materials will include information about the study and contact information, directing those interested to contact a research team member. For students who express interest and contact the research team member, another email will be sent, containing information about the study, research team

member contact information, and a link prompting students to complete an online consent and eligibility screening measure via REDCap. For those who do not respond to the recruitment email, a “nudge” email will be sent to remind participants 7 days after first contact. The consent form describes the study, discusses participant roles and responsibilities and risks, informs participants that their data will be confidential and de-identified data will be used for research purposes only, and provides important contact information. Participants will agree to participate by checking a “yes” box and typing in their name. Once consent is received, another email will be sent to schedule interviews with students and share Zoom meeting information. Reminder emails will be sent 24-48 hours in advance and day of. These recruitment procedures are similar to those that have been approved by the Northwestern University IRB for prior studies conducted by our lab group.

### **Procedures Involved:**

Monthly data on engagement with counseling center services will be collected from the counseling center’s Titanium Electronic Medical Record (EMR) to serve as a predeployment “baseline” for Phase 2. For the primary outcome of counseling center resource utilization, we will compare the predeployment phase (the 2 semesters prior to program implementation) to the implementation phases. During the predeployment phase, weekly data will be collected from existing service records at the counseling centers at UIC and NIU on new counseling appointments, follow-up appointment, group therapy appointments and crisis appointments. The data will be reported in aggregate and will not include individual personal identifiers. The SSM program will first be implemented in one study site (UIC or NIU – chosen via random selection) using the initial implementation plan (e.g. advertisements, identification of early adopters, identification of student leaders to serve as champions) designed in Phase 1. Data from individual interviews will be gathered from the first study site will inform an enhanced implementation plan. During this third semester, predeployment data will also be collected at Site #2. Then, the enhanced implementation plan, updated based on the semester 3 deployment at Site #1, will be deployed at both study sites and data will be collected for an additional semester. When the implementation begins on each campus, the program will be made freely available to download, and counseling center intake paperwork will be modified to ask students if they used the SSM program which allows for tracking of counseling center referrals while maintaining patient confidentiality. This design allows us to examine: a predeployment phase for both sites, an initial phase of implementation for Site #1, and an enhanced implementation phase for Site #1 and for Site #2. A strength of this implementation design is that it allows for learning within itself by comparing initial implementation strategies with an enhanced implementation plan. This process of learning and adapting is key for effective and sustainable implementation. Staggering the start times of implementation allows for within-site targeted comparisons of effect of introducing the SSM program on utilization of the counseling center in each site, and for an exploration of between-site differences in the impact of the enhanced implementation plan.

The study utilizes an interrupted time-series design, which offers a number of benefits over large-N designs and has been shown to be an acceptable approach for examining treatment efficacy as well as a useful design for rigorous implementation research when few sites are

involved. There are both scientific and pragmatic benefits to introducing a program into a system with this design approach. Since these time-series measurements are recorded on a weekly basis, one can observe how change unfolds across time, examine seasonal effects to better evaluate change in these centers that are often at capacity, and investigate the trajectory of change. Because all members of the campus community are granted access to the program, this design meets the needs of community stakeholders.

To examine outcomes for Hypothesis 2 (sustained use of the SSM program will result in reductions in depression and anxiety among individual users, and will be mediated by increases in mental health literacy, knowledge of mental health care services, and cognitive and behavioral coping skills), we will examine longitudinal data from individual users regarding depression and anxiety symptoms, mental health literacy, knowledge and beliefs about mental health care services, barriers to mental health care, and cognitive and behavioral coping skills to determine if sustained program use is associated with changes in these measures.

*SSM Program:* The program will prompt users to complete repeated symptom assessments and provide psychoeducation regarding current symptoms while encouraging students in need to utilize available campus services. Upon download, the Student Hub app will prompt users to complete the PHQ-8 and GAD-7 and will provide feedback on symptoms. Based on symptom scores, users will receive automated feedback about depression/anxiety, availability of mental health and wellness services on campus, and information and interactive digital tools to support continued stress management and wellness. Users will be prompted with ability to use interactive self-help tools within the app suite. Interactive, clinical apps (designed for daily use) are included to facilitate engagement with mood monitoring, and to appeal to a preference for self-reliance.

*Risks of the intervention:* The primary risk of the intervention is participants being distracted by their mobile phones while engaged in activities that demand their complete attention. Participants occasionally try to use mobile apps while driving motor vehicles, and therefore will be instructed never to use the mobile phone while driving. Participants will be made aware of the physical, financial, and legal risks associated with using the phone while driving. If the research team becomes aware of a participant engaging in this behavior, the PI and mentors will consult to determine the most appropriate way to eliminate this risk.

*Protection for risks of worsening mental or emotional state and or self-harm thoughts/events:* Some participants may show a worsening of depressive symptoms, suicidality or problems during the study period. Consistent with past research on internet-based mental health screening and intervention for college students, participants will receive automated messages information on available resources (e.g. local emergency services, the Crisis Text Line, National Suicide Prevention Lifeline, and on-campus crisis counseling). These are risks inherent in the population and would occur whether or not they were enrolled in the study. We do not believe that the risk of these depressive, suicidal, or other adverse outcomes are increased as a function of being enrolled in this study or receiving the mobile application. All potential risks associated with participation in this study will be disclosed in consent documents.

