**Statistical Analysis Plan:**

We used a mixed-methods approach to analyzing the impact of the IntelliCare for College Students program, in that we analyzed quantitative data on app usage and counseling center utilization alongside qualitative data generated through interviews with students and staff.

Demographic data were examined primarily in the form of descriptive statistics, and chi-square tests and a student's t-test were used to examine potential demographic differences between the participants who consented to the study that did (n=117) and did not (n=65) download and register their participant ID to the IntelliCare for College Students app. App usage data were examined in the form of descriptive statistics.

Due to missing data throughout the trial, multiple imputation methods and separate generalized linear mixed models to account for repeated measures from each participant over time, were used to examine symptoms of depression and anxiety at baseline, week 1, week 2, week 4, week 6 and week 8, and anxiety literacy, depression literacy, and cognitive and behavioral coping skills at baseline, month 1 and month 2.

To examine symptom assessments longitudinally, we fit the available weekly symptom assessment data into a structure of baseline, week 1, week 2, week 4, week 6 and week 8 timepoints. Only 2 individuals had complete data. A total of 48 participants only completed the symptom assessment at one time period, 16 (17) completed 2 of the 6 assessments (16 for GAD, 17 for PHQ), 3 (2) completed 3 of the 6 assessments, 5 had 4 of the 6 assessments, and 5 were missing just one assessment. Multiple imputation methods were used to account for missing data. Participants were also prompted to complete measures of our mental health intervention targets on a monthly basis within the app. Many participants did not complete these assessments, and data were examined at baseline, month 1, and month 2. Multiple imputation methods were used to account for missing data.

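### The Phase 2 symptom baseline is taken in the app after download, so at least 38 of 117 registrants and 103 of 182 consenters have none; the literacy and coping baseline can follow exposure

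*Combined protocol and SAP*

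**What the plan says.** The SSM Program paragraph of Procedures Involved describes one step at download: "Upon download, the Student Hub app will prompt users to complete the PHQ-8 and GAD-7 and will provide feedback on symptoms". It adds that, depending on their scores, "users will receive automated feedback about depression/anxiety, availability of mental health and wellness services on campus, and information and interactive digital tools".

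The Statistical Analysis Plan (SAP) derives the symptom timepoints from the in-app series: "we fit the available weekly symptom assessment data into a structure of baseline, week 1, week 2, week 4, week 6 and week 8 timepoints". On literacy and coping it says: "Participants were also prompted to complete measures of our mental health intervention targets on a monthly basis within the app". It continues: "Many participants did not complete these assessments, and data were examined at baseline, month 1, and month 2".

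Under Study-Wide Recruitment Methods, participants are sent to a website where "they will be able to access the study screening form and digital consent form". The content of that screening form is not listed for Phase 2 users. The Confidentiality section says that online assessments run on REDCap, but not which ones or when.

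The SAP compares demographics between "participants who consented to the study that did (n=117) and did not (n=65) download and register their participant ID" to the app.

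**The concern.** Two separate matters arise, and they affect different measures.

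The first is coverage. If the symptom baseline exists only inside the app, people who consent and never register have none, and neither do registrants who ignore the prompt. Registrants can then be compared with non-registrants on demographics alone. The trial cannot say whether more or less symptomatic students took up the program, although Resources Available gives uptake as the Phase 2 interest. Multiple imputation also has no symptom information to draw on for a registrant with no score.

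The second is order. The feedback informs users about depression and anxiety, campus services and self-help tools. This overlaps the mediators in Hypothesis 2: literacy, knowledge of services and coping. If the first literacy or coping measure comes after that feedback, any immediate learning is already in the baseline and is lost from the change to month 1 and month 2.

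**Working it through.** The documents state no figure for the number of people with a baseline, so there is none to reproduce. The counts below come from the SAP.

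**Step 1. Consenters.** 117 registered + 65 did not = 182.

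**Step 2. People with any symptom score.** Add the groups by number of timepoints completed:

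| Timepoints completed, of 6 | GAD | PHQ |
|---|---|---|
| 1 | 48 | 48 |
| 2 | 16 | 17 |
| 3 | 3 | 2 |
| 4 | 5 | 5 |
| 5 | 5 | 5 |
| 6 | 2 | 2 |
| Any | 79 | 79 |

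**Step 3. Bound on missing symptom baselines.** Baseline is one of the six timepoints, so the number with a baseline cannot exceed 79.

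- Registrants without one: at least 117 − 79 = 38, and 38/117 = 32.5%.
- Consenters without one: at least 182 − 79 = 103, and 103/182 = 56.6%. With all 79 among the registrants, these are 65 non-registrants + 38 registrants.

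The shortfall may be larger. The SAP does not say which timepoint the 48 people with a single score completed. Only the 2 complete cases certainly have a baseline. Those with two or more scores number 79 − 48 = 31, and 31/182 = 17.0%.

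**Step 4. Could a baseline from the online form change this?** If a symptom score had been taken from every consenter on the form and used as the baseline, all 182 would have at least one of the six timepoints. Only 79 do. So no such score fed this analysis.

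**Step 5. Literacy and coping, coverage.** No completion counts are given. If collection was in the app only, at least 65/182 = 35.7% of consenters have no score, plus the unquantified non-completers that the SAP mentions.

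**Step 6. Literacy and coping, order.** Set the two texts side by side. Procedures Involved names the PHQ-8 and GAD-7 at download, then feedback, and names no literacy or coping measure at that step. The SAP lists a literacy and coping baseline separate from month 1, prompted in the app, without placing it before or after feedback. If the true mean change is D and feedback raises the score by d before the first measurement, the measured change is D − d. The documents give no value for d.

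**The case against.** The strongest objection is that the order problem rests on silence. The SSM Program paragraph describes the program and is not an assessment schedule. It does not say that the two symptom scales are the only measures at download. A reader might infer that the literacy and coping baseline did come after feedback. The documents do not say so; they only fail to exclude it. Nor do they exclude that those measures were first taken on a REDCap form, although the SAP wording makes in-app collection more likely. This stands, and it limits the order point to a possibility.

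A reader might also infer that the symptom baseline is contaminated. It is not, on the described sequence: the first PHQ-8 and GAD-7 prompt precedes its feedback.

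The choice of denominator can also be challenged. Hypothesis 2 concerns individual users, so the 65 who never registered do not bias it. That is right. The 56.6% matters for describing uptake; for Hypothesis 2 the relevant figure is 32.5% of registrants, and a majority of registrants without a baseline is not shown.

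It can be said, too, that no hypothesis asks whether symptoms predict uptake, and that the primary outcome, counseling center utilization, is untouched. Both are true and limit the weight of the point. But Phase 2 is meant to pilot data collection and assessment procedures for a larger trial, so a weak baseline procedure is a proper finding here.

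Finally, the SAP is in the past tense with final counts. Pre-download scores cannot now be obtained from those participants. This stands and divides the fix into two parts.

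**Conclusion.** The concern holds in two parts of unequal strength.

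- **Coverage, established from the SAP counts.** At most 79 people have any symptom score, so at least 32.5% of registrants and 56.6% of consenters have no symptom baseline. This assumes that the listed groups are mutually exclusive and cover everyone with a score, and that all are consenters. The equal totals of 79 for the two scales support the first assumption.
- **Order, open.** The literacy and coping baseline can follow exposure. Shrinkage of the measured change would require both that it did and that one round of automated feedback raised the scores. This is more plausible for literacy than for coping skills, where nothing in the documents supports an immediate rise. A reader might want a percentage for the loss, but any figure would only restate an assumption about the immediate gain.

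This is a cheap improvement to a secondary part of a pilot. It does not affect the utilization analysis.

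**What to change.** **For further recruitment and the larger trial.** Amend Study-Wide Recruitment Methods and the SSM Program paragraph of Procedures Involved as follows:

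- Collect PHQ-8, GAD-7, anxiety literacy, depression literacy and coping on the existing online screening and consent form, before the download link is given.
- Ask on the same form whether the app has already been used. It is freely available, so a student may have met it before the form.
- Use these values as the baseline and in the imputation model.
- Compare registrants with non-registrants on baseline symptoms as well as demographics.

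The cost is a short amendment and some extra minutes on a form that already exists. The downside is that a longer form may lose a few consenters.

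**For data already collected.** State in the SAP or report when and where each baseline measure was taken relative to feedback, how many registrants have it, and its timing after download. Label any literacy or coping value taken after feedback as the first in-app assessment, not as baseline. This needs no new data beyond the app's time stamps, assuming these were kept.
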